8.5.2.1.3 Grading of Adverse Events

The severity of all adverse events, including all treatment-emergent clinically significant laboratory test results and all treatment-emergent clinically significant changes in laboratory test results, will be assessed in accordance with the following criteria:

- Mild (Grade 1): awareness of signs or symptoms that are easily tolerated, are of minor irritant type, cause no loss of time from usual activities, do not require medication or further medical evaluation, and/or are transient.
- Moderate (Grade 2): signs or symptoms sufficient to interfere with function but not activities of daily living.
- Severe (Grade 3): signs or symptoms sufficient to interfere with activities of daily living; signs and symptoms may be of a systemic nature or may require further medical evaluation and/or treatment.
- Life-Threatening (Grade 4): disabling or with life-threatening consequences. This definition does not include any event that might have caused death if it had occurred in a more severe form.
- Fatal (Grade 5): death related to an adverse event.

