8.5.2.1.4 Relationship to Study Drug

The relationship of the study drug to each adverse event will be determined by the Investigator based on the following definition:

- No reasonable causal relationship (probably not related): There is no plausible temporal relationship or there is another explanation that unequivocally provides a more plausible explanation for the event.
- Yes, reasonable causal relationship (possibly related): There is evidence in favor of a causal relationship; i.e., there is a plausible time course, and at least one of the following criteria apply:
 - There is a reasonable pharmacological relationship (or known class effect)
 - There is no other more plausible explanation

- There is a positive de-challenge (without active treatment of the event)
- There is a positive re-challenge
- There is a distinguishable dose effect

Within the reporting requirement under 21 CFR 312.32(c)(1)(i), the FDA provides the following examples of types of evidence that would suggest a causal relationship between the drug and the adverse event.

- A single occurrence of an event that is uncommon and known to be strongly associated with drug exposure (e.g., angioedema, hepatic injury, Stevens-Johnson Syndrome).
- One or more occurrences of an event that is not commonly associated with drug exposure, but is otherwise uncommon in the population exposed to the drug (e.g., tendon rupture).
- An aggregate analysis of specific events observed in a clinical trial (such as known consequences of the underlying disease or condition under investigation or other events that commonly occur in the study population independent of drug therapy) that indicates those events occur more frequently in the drug treatment group than in a concurrent or historical control group.

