6.2 Data Adjustments, Handling, Conventions

All collected data will be presented in listings. Data not subject to analyses according to this plan will not appear in any tables or graphics but will be included only in the data listings.

Adverse events will be coded using the Medical Dictionary for Regulatory Activities (MedDRA) (version 16.1). Concomitant medications will be coded using World Health Organization Drug Dictionary (WHO-DD) (version March 1, 2013).

If partial dates occur, the convention for replacing missing dates for the purposes of calculating derived variables is as follows:

For partial start dates:

- If the year is unknown, then do not impute the date but assign a missing value.
- If the month is unknown, then:
 - o If the year matches the year of enrollment date, then impute the month and day of the randomization date.
 - o Otherwise, assign 01 January
- If the day is unknown, then:
 - o If the month and year match the month and year of the enrollment date, then impute the day of the first dose date.
 - o Otherwise, assign 01

For partial end dates:

- If the year is unknown, then do not impute the date but assign a missing value.
- If the month is unknown, then assign the last day of the year, 31 December.

If the day is unknown, then assign the last day of the month.

If an AE has a missing severity, it will be imputed as 'Severe'; any missing relationship to study drug of an AE will be imputed as 'Related'. No other missing data will be imputed unless otherwise specified.

In general, for quantitative laboratory values reported as '<' or '≤', the lower limit of quantitation (LLOQ), or limit of detection (LOD), the reported value (i.e., LLOQ, LOD) will be used for analysis).

For quantitative laboratory values reported as '>' or '\geq', the upper limit of quantitation (ULOQ), the reported value (i.e., ULOQ) will be used for analysis.

For analysis purposes, repeat laboratory test results will not be used unless the original laboratory value is missing or indicated as invalid, in which case the first non-missing repeat

Protocol: HZNP-ACT-303 Page 12 of 19

Final Version 1.0

laboratory value will be used for data analysis.

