6.3 Derived and Computed Variables

The following derived and computed variables have been initially identified as important for the analyses of Safety and Efficacy endpoints. It is expected that additional variables may be required. The SAP will not be amended for additional variables that are not related to the primary target or key secondary target variables. Any additional derived or computed variables will be identified and documented in the SAS programs that create the analysis files. If the SAP is not amended, further derivations related to primary and secondary target variables will be described in the CSR.

- 303 Baseline = The last non-missing measurement/assessment on the date of Week 26
 Visit from HZNP-ACT-302. If this measurement is missing or otherwise unavailable, it
 will be the last non-missing measurement/assessment on or prior to first dose in HZNP ACT-303.
- Study Day = Assessment Date Date of Enrollment + 1
- Change from Baseline = Value at Post-Baseline Value at Baseline
- Concomitant Medication is defined as any medication a subject has received concurrently with study treatment.
- Prior Medication is defined as any medication or therapies initiated prior to date of first dose of study drug. Medications that are started prior to the date of first dose of study drug and continue after the first dose of drug are considered to be both prior and concomitant medications.
- Treatment-Emergent Adverse Event (TEAE) A TEAE is any adverse change from the subject's baseline condition that occurs on or after the date of the first dose of study drug through the duration of the clinical study.
- Related TEAE Any TEAE with a reported relationship to study drug of 'possibly related'.
- Compliance = Calculated as the percentage of the number of vials used divided by the expected number of vials used, where the number of vials used is the number of used vials returned.

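### The SAP's imputed causality label does not match its own definition of a related TEAE, and imputing every missing severity as Severe under-grades an event recorded as fatal, life-threatening or disabling

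*SAP*

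**What the plan says.** **Causality.** Protocol 8.5.2.1.4 gives the investigator two categories: "No reasonable causal relationship (probably not related") and "Yes, reasonable causal relationship (possibly related"). SAP 6.2 deals with blanks: "any missing relationship to study drug of an AE will be imputed as 'Related". SAP 6.3 defines a related TEAE as "Any TEAE with a reported relationship to study drug of 'possibly related".

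**Severity.** Protocol 8.5.2.1.3 grades events from 1 to 5. The top three levels are "Severe (Grade 3): signs or symptoms sufficient to interfere with activities of daily living", "Life-Threatening (Grade 4): disabling or with life-threatening consequences" and "Fatal (Grade 5): death related to an adverse event". SAP 6.2 has one rule for a blank: "If an AE has a missing severity, it will be imputed as 'Severe". It makes no exception for serious or fatal events.

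**Use.** SAP 9.1 tabulates TEAEs by relationship and by severity. Within a preferred term it keeps each subject's strongest relationship or maximum intensity. SAEs are tabulated by system organ class and preferred term, and SAP 9.1.1 gives deaths their own summary and listing.

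**The concern.** Both imputation rules are meant to be worst-case rules, and neither is fully specified as one. The causality rule assigns a label that the collected scale does not contain, and the definition it should feed asks for a reported value with a different label. The severity rule stops at the middle of a five-grade scale, even when other data on the same event show that a higher grade applies.

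Long-term safety is the study's only objective (protocol 7.1, SAP 2.1.1), and SAP section 8 drops all efficacy analysis. The TEAE tables by relationship and by severity are therefore among the main outputs. Two programmers working from this text could produce different related-TEAE counts. The severity table could also disagree with the death and SAE outputs.

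**Working it through.** The plan gives no figure to reproduce, so the check traces each rule through to the tables.

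**Causality**
1. Start with a TEAE whose relationship field is blank.
2. SAP 6.2 sets the value to *Related*.
3. SAP 6.3 asks whether the relationship was reported and whether it is *possibly related*. The value was imputed, not reported, and its label is different. Read literally, the event fails on both counts and is not a related TEAE.
4. In the by-relationship table of SAP 9.1 the event sits in a third level beside the two protocol levels. The SAP does not say how that level ranks against *possibly related* when the strongest relationship per preferred term is chosen. The row in which such a subject appears is therefore undefined.
5. Without any imputation the event would also be outside the related count. On the literal reading, the rule leaves that count unchanged.

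**Severity**

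The imputed grade is 3, so the error is 3 minus the true grade:

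| True grade | Imputed | Error |
|---|---|---|
| 1 Mild | 3 | 3 − 1 = +2 |
| 2 Moderate | 3 | 3 − 2 = +1 |
| 3 Severe | 3 | 0 |
| 4 Life-Threatening | 3 | 3 − 4 = −1 |
| 5 Fatal | 3 | 3 − 5 = −2 |

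The rule overstates blanks that were truly mild or moderate. It understates only Grades 4 and 5. For those, the higher grade may already be visible, because death, life threat and significant disability are all seriousness criteria in protocol 8.5.2.1.1. Unless the same subject has a higher-graded event of the same preferred term, the imputed Grade 3 is what the severity table shows.

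**Size**

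The documents give neither a rate of blank fields nor the number of subjects N. If *Related* was meant as *possibly related*, the literal reading lowers the related-TEAE percentage by 100/N points for each subject with no other related TEAE. For illustration only:
- N = 14 gives 100/14 = 7.1 points. Fourteen is the number who had entered HZNP-ACT-302 by 10 March 2016 (protocol 6.2). It is not a forecast or a floor for this study.
- N = 90 gives 100/90 = 1.1 points. Ninety is an assumption with no source in the documents.

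**The case against.** The strongest reply on causality is that SAP 6.2 and 6.3 can be read together. *Related* in 6.2 echoes the SAP's own term *Related TEAE*: 6.3 says which reported value belongs to that class, and 6.2 sends missing values there too. The scale has only one positive category, so *Related* has only one sensible target. This is probably the intent. It remains an inference, because the SAP never equates the two labels and the word *reported* in 6.3 points the other way.

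On severity, a blank grade on a fatal or life-threatening event should be rare. Protocol 8.5.2.1 requires severity and causality to be assessed for every event, section 9 requires a signed assessment, section 11 provides for source data verification, and section 12 for queries on omissions. If a blank survived, the death would still appear under SAP 9.1.1, and a fatal or life-threatening event would appear in the SAE tables. This stands: no death is hidden, and the effect is confined to the severity table.

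A reader might infer three stronger things, which the documents do not support:
- **That events are removed from the related count.** A blank was never in that count, and the event stays visible in the by-relationship table and in the listing of all AEs.
- **That serious events are downgraded.** There is no reported grade to lower; a missing grade is filled in too low.
- **That both rules favour the drug.** Severe overstates blanks that were truly mild or moderate, so the severity rule has no uniform direction. The causality rule, at worst, equals no imputation as far as the related count is concerned.

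**Conclusion.** The point holds as a specification inconsistency with a probably very small effect. Taken literally, SAP 6.2 and 6.3 leave imputed events outside the defined related-TEAE count and create a level that the protocol scale does not have. The single severity rule is a reasonable default, but it gives too low a grade (by one for life-threatening or disabling events, by two for fatal ones) when recorded data already show the higher grade. The severity table would then disagree with the death summary or with the seriousness data behind the SAE tables.

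The causality conclusion rests on the literal wording of 6.3. The severity conclusion applies only if such an event reaches database lock without a grade. The number of events affected cannot be computed from the documents, and the 100/N figures only illustrate scale.

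**What to change.** 1. **SAP 6.2, causality:** impute a missing relationship as *possibly related*.
2. **SAP 6.3:** define a related TEAE as one whose relationship is reported as *possibly related* or is imputed as such under 6.2.
3. **SAP 6.2, severity:** set a missing severity to Fatal (Grade 5) if the recorded outcome is death, to Life-Threatening (Grade 4) if recorded seriousness data show a life-threatening or disabling event, and to Severe (Grade 3) otherwise. Disabling must be named because the protocol's Grade 4 covers it.

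The cost is a few sentences of SAP text and a few lines of programming, made before database lock. No clinical procedure changes. The eCRF is not among the documents, so the sponsor should confirm that outcome and seriousness are held as usable fields there or on the SAE form. The related and Grade 4–5 counts may rise slightly.

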6.3 Derived and Computed Variables

The following derived and computed variables have been initially identified as important for the analyses of Safety and Efficacy endpoints. It is expected that additional variables may be required. The SAP will not be amended for additional variables that are not related to the primary target or key secondary target variables. Any additional derived or computed variables will be identified and documented in the SAS programs that create the analysis files. If the SAP is not amended, further derivations related to primary and secondary target variables will be described in the CSR.

- 303 Baseline = The last non-missing measurement/assessment on the date of Week 26
 Visit from HZNP-ACT-302. If this measurement is missing or otherwise unavailable, it
 will be the last non-missing measurement/assessment on or prior to first dose in HZNP ACT-303.
- Study Day = Assessment Date Date of Enrollment + 1
- Change from Baseline = Value at Post-Baseline Value at Baseline
- Concomitant Medication is defined as any medication a subject has received concurrently with study treatment.
- Prior Medication is defined as any medication or therapies initiated prior to date of first dose of study drug. Medications that are started prior to the date of first dose of study drug and continue after the first dose of drug are considered to be both prior and concomitant medications.
- Treatment-Emergent Adverse Event (TEAE) A TEAE is any adverse change from the subject's baseline condition that occurs on or after the date of the first dose of study drug through the duration of the clinical study.
- Related TEAE Any TEAE with a reported relationship to study drug of 'possibly related'.
- Compliance = Calculated as the percentage of the number of vials used divided by the expected number of vials used, where the number of vials used is the number of used vials returned.

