⁸ Subjects who are not able to receive direct-to-home study drug shipments will return to the clinic for interim clinic visits three months after the Baseline and 6-month assessment visits; those who are able to receive direct-to-home shipments will be contacted by telephone.

⁹ Perform at clinic visits only; those with telephone visits will receive/return study drug supplies at next clinic visit.

¹⁰ Subjects who complete the study will undergo final assessments while still on study drug and will then be transitioned to commercial product. Subjects who prematurely withdraw from the study will have the EOS assessments completed within two weeks of study drug discontinuation. In the event the Sponsor decides to discontinue development for the treatment of FA, all subjects will be contacted and instructed to return to the clinic for final assessments while still on active drug.

¹¹ For statistical purposes, the last on-treatment visit from HZNP-ACT-302 (Visit 26) will be used to assess changes to the EOS assessment in this study.

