8.5.2.3 Vital Signs

Vital signs (resting systolic and diastolic blood pressure in the non-dominant arm, pulse, and temperature) will be assessed at Baseline/Day 1, each subsequent 6-month assessment clinic visit, and the EOS (or PW) Visit. Blood pressure and pulse measurements will be obtained with the subject's arm unconstrained by clothing or other material and while the subject is sitting up. When possible, the same arm will be used for measurements in all study visits. Temperature will be obtained orally or via the ear.

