8.5.2.5 Clinical Laboratory Tests

Samples of blood (4.5 mL) and urine are scheduled for collection at Baseline/Day 1, each 6-month assessment clinic visit, and the EOS (or PW) Visit. Additional follow-up samples for clinical laboratory testing should be obtained as clinically indicated.

All clinical laboratory testing, with the exception of on-site urine pregnancy tests during the treatment period for females of childbearing potential, will be performed by the central clinical safety laboratory (URMC).

The following clinical laboratory tests will be performed:

- Complete blood count
- Chemistry panel
- Urinalysis

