8.5.4.4 End-of-Study or Premature Withdrawal Visit

At the time ACTIMMUNE becomes commercially available or if development is ceased for the treatment of FA, subjects will return to the clinic while still on active study drug for an EOS Visit prior to transitioning to the commercial product or discontinuing study drug. Subjects who prematurely withdraw from the study will have EOS assessments completed within two weeks of study drug discontinuation. Clinic staff will perform the following procedures at the Final/EOS visit:

- Collect all used, partially used, and unused study medication kits and vials from previous clinic visit.
- Perform brief physical examination, including vital signs.
- Collect blood (4.5 mL) and urine samples for safety clinical laboratory values (including urine pregnancy test [if applicable]).
- Enquire about adverse events and concomitant medication use.
- Perform FARS.
- Perform ECG.

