8.6.2 Safety Variables

Adverse event and concomitant medication data will be summarized. Vital sign and clinical safety laboratory data will be summarized with descriptive statistics for Baseline, post-dose, and change from Baseline to post-dose values, and shift tables will be presented for clinical laboratory values from Baseline to each post-dose visit. The ECG statistical analysis will use the same approach as described above for the FARS analysis.

Physical examination findings will be listed by subject.

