2.2.1 Safety Endpoints

Adverse event and concomitant medication data will be summarized. Clinical laboratory safety data, vital sign data, and ECG interval data will be summarized with descriptive statistics for

Protocol: HZNP-ACT-303 Page 8 of 19

Final Version 1.0

Baseline of HZNP-ACT-303, post-dose, and change from Baseline of HZNP-ACT-303 to post-dose values. Shift tables will be presented for clinical laboratory values and ECG categorical results from Baseline of HZNP-ACT-303 to each post-dose visit. Physical examination findings will be listed by subject.

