- ⁵ Only for female subjects of childbearing potential.
- 6 The Day 1 Visit of this study (HZNP-ACT-303) occurs on the same day as the EOS Visit (Week 28 Follow-Up Visit) for HZNP-ACT-302.
- Findings will be recorded for both the Day 1 (Baseline) Visit of this study and the Week 28 Follow-up Visit for HZNP-ACT-302.
- Subjects who are not able to receive direct-to-home study drug shipments will return to the clinic for interim clinic visits three months after the Baseline and 6-month assessment visits; those who are able to receive direct-to-home shipments will be contacted by telephone.
- ⁹ Perform at clinic visits only; those with telephone visits will receive/return study drug supplies at next clinic visit.
- Subjects who complete the study will undergo final assessments while still on study drug and will then be transitioned to commercial product. Subjects who prematurely withdraw from the study will have the EOS assessments completed within two weeks of study drug discontinuation. In the event the Sponsor decides to discontinue development for the treatment of FA, all subjects will be contacted and instructed to return to the clinic for final assessments while still on active drug.

¹¹ For statistical purposes, the last on-treatment visit from HZNP-ACT-302 (Visit 26) will be used to assess changes to the EOS assessment in this study.

Changes in medical history from the Baseline of HZNP-ACT-301 will be recorded on the electronic case report forms. The medical history from the HZNP-ACT-301 study will be available for reference.

Subjects will be given a 3-month supply of study drug at each clinic visit and an additional 3-month supply will be directly shipped to the subjects' home in between the required 6-month clinic visits. If direct shipments are not feasible, subjects will return to the clinic every three months to obtain study drug; however, assessments (other than adverse event queries) will only be performed every six months.

Protocol: HZNP-ACT-303 Page 10 of 19

Final Version 1.0

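### SAP 6.3 applies one Week 26 (HZNP-ACT-302) baseline to laboratory and vital-sign changes, where the protocol and the SAP's own Table 1 use Day 1, and the change is not declared

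*SAP*

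**What the plan says.** **Protocol.** Baseline is the Day 1 visit, held on the same day as Week 28 of HZNP-ACT-302 (section 2.1). Section 8.5.2.5 states: "Samples of blood (4.5 mL) and urine are scheduled for collection at Baseline/Day 1". Section 8.5.2.3 says that vital signs "will be assessed at Baseline/Day 1, each subsequent 6-month assessment clinic visit". Section 8.6.2 plans the analysis: "Vital sign and clinical safety laboratory data will be summarized with descriptive statistics for Baseline, post-dose, and change from Baseline to post-dose values", with laboratory shift tables from the same Baseline.

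ECG and FARS are handled differently because neither is done at Day 1. Footnote 11 of the schedule, attached only to those two rows, reads: "For statistical purposes, the last on-treatment visit from HZNP-ACT-302 (Visit 26) will be used to assess changes to the EOS assessment in this study". Sections 8.6.1 and 8.6.2 repeat this for FARS and ECG.

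**SAP.** Table 1 (section 3) keeps the same split. Its Baseline column is Day 1, with laboratory tests and vital signs marked, and footnote 6 says: "The Day 1 Visit of this study (HZNP-ACT-303) occurs on the same day as the EOS Visit (Week 28 Follow-Up Visit) for HZNP-ACT-302". Footnote 11 again sits only on ECG and FARS.

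Section 6.3 then gives a single definition: "303 Baseline = The last non-missing measurement/assessment on the date of Week 26" visit of 302. If that value is missing or unavailable, the last value on or before the first 303 dose is used. Section 2.2.1 applies the 303 baseline to laboratory, vital-sign and ECG changes, and adds: "Shift tables will be presented for clinical laboratory values and ECG categorical results from Baseline of HZNP-ACT-303 to each post-dose visit". Section 10 lists only the removal of the efficacy analyses.

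**The concern.** The two candidate baselines answer different questions. The protocol calls Week 26 of 302 the last on-treatment visit, so a Week 26 value is an on-drug value. Day 1 of 303 falls two weeks later, before 303 dosing starts. A change from Day 1 shows what happens when treatment resumes and continues. A change from Week 26 shows what further exposure adds to an effect already present.

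Long-term safety is the only objective. The label appended to the protocol describes reversible neutropenia and thrombocytopenia, and transaminase elevations that reverse when dosing is reduced or interrupted. Effects of that kind are the ones an on-drug baseline tends to cancel.

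Three consequences follow wherever Week 26 laboratory or vital-sign values exist:

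- A reversible effect at a stable dose has an expected change of about zero, and the shift table becomes symmetric.
- A withdrawal visit can look like improvement. Protocol 8.5.4.4 says: "Subjects who prematurely withdraw from the study will have EOS assessments completed within two weeks of study drug discontinuation". SAP 6.1 assigns that visit's data to the nearest scheduled visit, where they are summarized with on-drug values.
- The fallback gives some subjects an on-drug baseline and others, by inference, an off-drug one in the same table.

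A reader of Table 1 would take the tables to be changes from Day 1, while a programmer following 6.3 would produce changes from Week 26.

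**Working it through.** The plan gives no figure to reproduce on this point. The check has two parts.

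**1. The definitions side by side**

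| Variable | Protocol | SAP Table 1 | SAP 6.3 |
|---|---|---|---|
| Laboratory tests | Day 1 | Day 1 | Week 26 of 302; last pre-dose value if missing |
| Vital signs | Day 1 | Day 1 | Week 26 of 302; last pre-dose value if missing |
| ECG | Week 26 of 302 | Week 26 of 302 | Week 26 of 302; last pre-dose value if missing |

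The ECG entry agrees throughout, apart from the fallback. The laboratory and vital-sign entries do not. Section 6.3 is not quite universal, because SAP 7.3 takes demographics and baseline efficacy characteristics from HZNP-ACT-301, but that does not touch the conflict.

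*Drug status at Day 1.* The gap is 28 − 26 = 2 weeks = 14 × 24 = 336 h. The appended label (section 12.3) gives a subcutaneous half-life of 5.9 h, and 336 / 5.9 = 56.9, about 57 half-lives. If dosing stopped at Week 26, drug is gone by Day 1. This shows clearance; recovery of a laboratory effect is a further assumption.

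**2. Size, as an illustration only**

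Every input is assumed. ALT is lognormal with off-drug median 22 and upper limit of normal (ULN) 40. The log-SD is 0.30 between and 0.18 within subjects. A constant on-drug multiplier k is 1.3 or 1.5, with full reversal by Day 1.

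- Total log-SD: √(0.30² + 0.18²) = √0.1224 = 0.350. Correlation of two visits on the log scale: 0.0900 / 0.1224 = 0.735.
- Off-drug mean: 22 × exp(0.1224 / 2) = 23.39.
- Mean change at an on-drug visit from Day 1: 23.39 × (k − 1) = 7.0 (k = 1.3) or 11.7 (k = 1.5). From Week 26: 23.39 × (k − k) = 0.0.
- Above ULN at an on-drug visit: P(Z > ln(40 / 22k) / 0.350) = 16.9% or 29.1%, whichever baseline is used.
- Shifts are bivariate normal probabilities with correlation 0.735. With a share p of subjects on a Week 26 baseline, each result is (1 − p) × the Day 1 result + p × the Week 26 result.

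| On-drug visit | p = 0% (all Day 1) | p = 50% | p = 100% (all Week 26) |
|---|---|---|---|
| k = 1.3: mean change | +7.0 | +3.5 | 0.0 |
| k = 1.3: normal-to-high | 13.4% | 10.4% | 7.3% |
| k = 1.3: high-to-normal | 0.9% | 4.1% | 7.3% |
| k = 1.5: mean change | +11.7 | +5.8 | 0.0 |
| k = 1.5: normal-to-high | 25.1% | 17.6% | 10.1% |
| k = 1.5: high-to-normal | 0.4% | 5.2% | 10.1% |

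With no drug effect (k = 1.0), both baselines give 2.6% in each direction, so the difference comes from the drug effect.

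*Withdrawal visit, fully off drug.* From Week 26 the mean change is 23.39 × (1 − k) = −7.0 or −11.7, with 13.4% or 25.1% moving high-to-normal. From Day 1 it is 0.0, with 2.6% high-to-normal.

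*Sensitivity.* If only half the effect has reversed by Day 1, the mean change from Day 1 is 23.39 × (k − 1) / 2 = +3.5 or +5.8, so the contrast halves. If the effect itself halves during 303 after a dose change, the mean change is −3.5 or −5.8 from Week 26 and, with full reversal at Day 1, +3.5 or +5.8 from Day 1: opposite signs from the same data.

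**The case against.** The strongest objection is that the consequence may never arise. The 302 schedule is not in these documents. The Week 26 assessments they mention are FARS, ECG and a urine pregnancy test. If no laboratory or vital-sign values were taken at Week 26, the fallback normally returns Day 1, and the SAP and protocol agree in practice. This stands as a limit on impact. It does not rescue the text, which makes Week 26 the first choice and contradicts Table 1.

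Second, an on-drug reference can be defended. Day 1 is not treatment-naive, a change from Day 1 reflects re-exposure after a short gap, and the protocol itself uses Week 26 for one safety variable, ECG. Keeping Week 26 and declaring it would remove the inconsistency. That is a fair argument for showing the comparison. But the SAP gives no reason for the change, and as a replacement it drops the contrast the protocol planned.

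Third, the illustration is not evidence about this trial. Its inputs are assumed, full reversal by Day 1 is the influential one, and a fully off-drug withdrawal visit is the extreme case because two weeks is an upper limit. This is accepted: the figures show direction and mechanism only.

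Finally, the study tests no hypothesis and reports an abbreviated safety CSR. Absolute values, out-of-range counts by visit, listings and adverse event tables do not depend on this baseline. That limits the severity but leaves the change and shift tables misdefined.

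**Conclusion.** The concern holds. SAP 6.3 conflicts with the protocol and with the SAP's own Table 1 on the baseline for laboratory tests and vital signs, and section 10 does not declare it. That part rests on the text alone and is certain. Week 26 for ECG is the protocol's own choice and is not in question.

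The practical effect is conditional on Week 26 values existing, on dosing having stopped at Week 26, and on the effect reversing by Day 1. Under those conditions, the planned contrast of pre-dose with on-drug values becomes on-drug with on-drug, and a stable reversible effect disappears from mean change. With partial reversal the loss is smaller. The size for this trial cannot be computed from the documents. The point should be corrected before the tables are programmed, but it does not hide safety signals from the outputs that are independent of baseline.

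**What to change.** In SAP 6.3, define baseline by variable:

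- Laboratory tests and vital signs: the last value on or before the first 303 dose, which is normally Day 1. Flag any subject whose value comes from an earlier visit, since this rule could otherwise pick up a Week 26 value when Day 1 is missing.
- ECG: Week 26 of 302, as in the protocol.
- State the rule for the baseline physical examination, which is scheduled at Day 1. Do the same for weight, height and BSA, whose changes SAP 9.3 summarizes although the Day 1 vital-sign row does not list them.

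If a Week 26 comparison of laboratory and vital-sign data is wanted, present it as supportive and declare it in section 10 with the reason. A further set of changes from the last value before first ACTIMMUNE in 301 or 302 is optional.

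The cost is SAP wording and a change to the baseline flag; Day 1 laboratory and vital-sign data are already scheduled. The downside is that changes may look less favourable and will reflect re-exposure after about two weeks, which is a reason to keep the Week 26 comparison alongside. The fix does not alter the assignment of withdrawal visits in SAP 6.1, so off-drug withdrawal values would still be summarized with on-drug ones.
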